8.1.2. Nasal Self-swab

Participants will need to complete two nasal self-swabs.

Collection of Self-swab #1

Participants will need to perform Self-swab #1 as soon as possible, once they receive the home collection kit.

The collection of Self-swab #2 might occur at 2 different points in the study:

- a) If participant develops new or increased symptoms, the participant will perform Self-swab #2 (after Self-swab #1 and before day 42). Self-swab #2 Criteria: An illness involving any 1 or more of the following symptoms will trigger self-swab collection:
 - New or increased fever
 - New or increased cough
 - New or increased shortness of breath or difficulty breathing.
 - New or increased fatigue
 - New or increased nasal congestion
 - · New or increased runny nose
 - · New or increased sore throat
 - New or increased loss of taste or smell
 - New or increased chills
 - New or increased rigors
 - New or increased muscle pain
 - New or increased diarrhea
 - New or increased vomiting
 - New or increased headache
 - New or increased nausea
 - New or increased wheezing
- b) If participant does not develop any new or increased symptoms, the participant will be asked to self-swab at day 42.

Detailed instructions on collection, processing, storage, and shipment for the nasal self-swab and contact information will be provided to the participant.

Depending on the results of the self-swab, the following results will determine the end of study for the participant (positive and negative refer to all viruses tested):

- a) All negative or invalid results from self-swab #1 and #2, the participant will stop the study at approximately the end of week 6.
- b) Any positive self-swabs #1 or #2, the participant will continue the study until end of Week 8.
- c) If both self-swabs are invalid the participant will exit the study at approximately the end of Week 6.

d) If one self-swab is negative and another is invalid, the participant will exit the study at approximately the end of Week 6.

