1. INTRODUCTION

This Appendix to the X9001293 SAP provides the detailed methodology for summary and statistical analyses related to the development of the screening algorithm for Symptomatic COVID-19 illness using voice features and symptoms data collected in the X9001293 study.

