3. ANALYSIS SETS (POPULATIONS FOR ANALYSIS)

Data for all participants will be assessed to determine if participants meet the criteria for inclusion in each analysis population prior to releasing the database and classifications will be documented per standard operating procedures.

Algorithm Population	Description
Full Analysis Set (FAS) as per the Main SAP	All participants who sign the informed consent document and enroll in the study, as defined in the main SAP. Qualified participants are males or females aged 18 years and older (or the minimum state-specific age of consent if > 18) at Screening visit, who are willing and able to comply with daily symptom and voice assessments on the Electronic Diary application and other study procedures including self-collection of nasal swabs, are expected to be available for the duration of the study, and are capable of giving informed consent.
Primary Analysis Set	Participants in FAS who have a negative RT-PCR test (at swab #1) and no acute symptoms (as determined by the enrollment questionnaire), and who become positive for SARS-CoV-2, influenza virus, or RSV (at swab #2) and symptomatic during the study.
Secondary Analysis Set A	Participants in FAS who have a negative RT-PCR test (at swab #1) and a negative RT-PCR test (at swab #2) irrespective of symptoms.
Secondary Analysis Set B	Participants in FAS who have a positive SARS-CoV-2, influenza virus, or RSV RT-PCR test (at swab #1) and are symptomatic.
CCI [REDACTED]	[REDACTED]

For the purpose of algorithm development and testing, the sick and well states are defined for each of the analysis sets (when applicable).

For Primary Analysis Set

The **sick state** is defined by considering a window of Electronic Diary data around a positive RT-PCR test at swab #2.

To determine the start of the sick state window, consider the difference in symptoms between consecutive recordings. The start of the sick window will be a symptom increase within 3 days prior to swab 2. If there is no symptom increase within these 3 days, the start of the window will be on swab #2 day.

If the number of days between swab #1 and swab #2 is less than or equal to 3, the sick state window will start on swab #2 day.

The *end of the window* is after swab #2 and defined by either:

- a. The last time the total symptom score is above 40% of the maximum total symptom score, or
- b. The final available datapoint if the total symptom score stays above 40% of the maximum score.

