If the total symptom remains below 40% of the maximum total symptom score after swab #2, the end of the window will be the swab #2 day.

The **well state** is defined by considering a window of Electronic Diary data around a negative RT-PCR test at swab #1, from 8 days before swab #1 up to 14 days before a positive swab #2. If there are less than 14 days between swab #1 and swab #2, the well state window ends on the day of swab #1.

For Secondary Analysis Set A

The **well state** is defined by considering an:

- Analysis time window from 8 days before swab #1 up to 8 days after swab #1.
- Analysis time window of 8 days up to and including swab #2.

For Secondary Analysis Set B

The **sick state** is defined by considering an analysis time window of 3 days before and 3 days after swab #1, including swab #1 day.

CCI

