5.5. Further Model Testing

5.5.1. Model Testing on RT-PCR Negative Participants

- Analysis Set: Participants in Secondary Analysis Set A to test models trained on the Primary Analysis Set ([Section 3](#)).
- Statistical Method: (a) As listed in [Section 4.6](#)., the best-performing output model from the classical machine learning ([Section 4.2.5](#)), deep learning ([Section 4.2.6](#)), fusion method ([Section 4.3](#)) and well vs. sick analysis with sick state definition centered around maximum total symptom score method ([Section 4.4](#)) will be tested on negative cases to estimate the false positive rate of the models. (b) The best performing Change From Baseline model will also be tested on analysis set above.
- Summaries: The following results will be generated for the specified analysis set (data permitting):
 - Confusion matrix will be tabulated and a listing of the performance measures provided for the two models (a) and (b).
 - Table of values of *specificity* as a function of Total Symptom Score thresholds for both models.
 - Plot of *specificity* against Total Symptom Score thresholds for both models.

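### The false positive rate in RT-PCR-negative participants pools symptom-triggered days with healthy days as 'well', so it does not reliably show separation of target illness from other illness

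*SAP*

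**What the plan says.** - **Membership.** adSAP Section 3 defines Secondary Analysis Set A as "Participants in FAS who have a negative RT-PCR test (at swab #1) and a negative RT-PCR test (at swab #2) irrespective of symptoms".
- **Label.** The only state visible for this set is the well state, made of two windows: "Analysis time window from 8 days before swab #1 up to 8 days after swab #1" and "Analysis time window of 8 days up to and including swab #2".
- **Swab #2.** Protocol 8.1.2 states: "An illness involving any 1 or more of the following symptoms will trigger self-swab collection". Sixteen symptoms are listed. Otherwise: "If participant does not develop any new or increased symptoms, the participant will be asked to self-swab at day 42". Set A applies one well rule to both kinds of swab.
- **Use.** In adSAP 5.5.1 the models "will be tested on negative cases to estimate the false positive rate of the models". That section also plans a table and a plot of specificity against Total Symptom Score thresholds.
- **Cases.** In the Primary Analysis Set the sick state starts at a symptom increase up to 3 days before swab #2, or on the swab day. It runs until the score last exceeds 40% of its maximum. The well state comes from the same participants, around their negative swab #1.
- **Targets.** adSAP 4.1 makes an observed sensitivity of 70% the success criterion and sets a minimum specificity of 60%, with no split by symptoms.
- **Purpose.** adSAP Section 1 describes "development of the screening algorithm for Symptomatic COVID-19 illness". adSAP 4.1 speaks of screening the general population, and Protocol 9.2 of early detection of upper respiratory illnesses.

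**The concern.** A participant who catches a cold from another virus reports symptoms, takes swab #2 and tests negative. The days up to that swab then enter Set A as well days, beside the days of people who felt nothing. The models are trained on cases' sick days against the same people's earlier well days. Set A is therefore where one would learn whether a model recognises SARS-CoV-2, influenza or RSV, or only recognises being ill. If healthy days dominate the pool, a model that does only the latter can still show a respectable specificity, and the study could be read as supporting target-virus detection when it supports only illness detection. The pooled figure also moves with the symptomatic share and the window lengths. The SAP's summary of changes gives dependence on sample mix as its reason for dropping the predictive values.

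**Working it through.** **1. The plan's own sizing.** adSAP 4.1 sizes sensitivity only. Cases for 70% ± 10% at 95%: 1.96² × 0.70 × 0.30 / 0.10² = 80.67, so 81, as stated. Half-width with 100 cases: 1.96 × √(0.21/100) = 8.98%, as stated. There is no counterpart for specificity or for Set A.

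**2. Days in the pool.** Swab #1 falls on Day 2 to Day 8 (Protocol 1.3). With the diary starting on Day 1, the swab #1 window holds 10 to 16 diary days. The swab #2 window adds 8, giving 18 to 24 in all if the windows do not overlap.

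**3. Share of ill days.** The documents give neither the symptomatic share *s* among double negatives nor the delay from onset to swab, so both are assumed.

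A simple count with *k* ill days per symptomatic participant is *s* × *k* / days. Averaged over swab #1 on Days 2 to 8, 1/days is 0.0481. Then *s* = 20%, *k* = 1 gives 1.0%, and *s* = 60%, *k* = 3 gives 8.6%.

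A simulation (40,000 participants per cell) took swab #1 uniform on Days 2–8, onset uniform from the day after swab #1 to Day 42, a 7-day illness, and overlapping window days counted once. Ill share of the days labelled well:

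| Onset to swab | s = 10% | s = 25% | s = 50% | s = 100% |
|---|---|---|---|---|
| 0–1 day | 1.0% | 2.6% | 5.4% | 11.5% |
| 0–3 days | 1.4% | 3.5% | 7.3% | 15.4% |
| 0–6 days | 2.0% | 5.0% | 10.2% | 21.4% |

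The lowest cell run (*s* = 5%, swab on the onset day) gave 0.4%. A 14-day illness changes little: 7.4% at *s* = 50%, delay 0–3 days. Healthy days are thus about 79% or more of the pool in every simulated cell.

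A bounding case lies outside this range. If everyone is symptomatic and all 8 days before swab #2 are ill, the share is 8/24 = 33% to 8/18 = 44%.

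**4. Effect on specificity.** Pooled specificity = (1 − f) × S_healthy + f × S_ill, where f is the ill share. Take a model that flags any illness at the 70% sensitivity target, so S_ill = 30%, with S_healthy = 70%. The formula becomes 0.70 − 0.40 f.

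- f = 0.0733 (*s* = 50%, delay 0–3 days): 67.1%
- f = 0.1544 (*s* = 100%, delay 0–3 days): 63.8%
- f = 0.2135 (*s* = 100%, delay 0–6 days): 61.5%
- Bounding case, f = 33% to 44%: 56.7% to 52.2%

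The figure reaches 60% at f = (S_healthy − 0.60)/(S_healthy − 0.30): 25% for S_healthy = 70%, 14% for 65%, 40% for 80%.

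**5. Illness phase.** The cases' sick window can run on past swab #2. Set A's second window stops on the swab #2 day. Illness days after it enter Set A only when swab #2 falls soon enough after swab #1 for them to lie within 8 days of swab #1. Ill negatives and ill positives are mostly not observed at the same phase.

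**6. Precision after a split.** With one observation per participant, 60% ± 10% needs 1.96² × 0.24 / 0.01 = 92.2, so 93 symptomatic negatives. Half-widths at 60% are 13.6 points for 50, 9.6 for 100, 6.1 for 250 and 3.0 for 1000. The documents do not say how many are available.

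**The case against.** The other side has real points.

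- **The symptom-score table.** adSAP 5.5.1 already breaks specificity down by symptom burden, so a reader who inferred that the plan cannot show separation would go too far. It is a partial remedy: no thresholds, direction, n or interval are stated, a raw score mixes chronic symptoms with new illness, and most illness days after swab #2 are absent.
- **The negative label.** A positive call in an RT-PCR-negative person is a correct false positive against the reference standard, and a pooled figure has some relevance to general-population screening. That stands. The weakness is the pooling under one well label.
- **The 60% figure.** It is a general target, not a pass mark for Set A. Specificity is also computed in the Primary Analysis Set, and the stated success criterion is sensitivity. The comparison above is an illustration, not a test of a rule in the plan.
- **The ill share.** It is tempting to call the rate almost entirely a healthy-day figure. The documents do not support that. A trigger of any one of 16 symptoms could make the symptomatic share large, and late swabs add ill days. Set A also does not exclude acute symptoms at enrollment, which the simulation ignores. Nor must every window contain the onset, since a late swab can leave it outside the 8 days.
- **Unseen text and status.** Parts of adSAP 3 and 4.6, and what appear to be Sections 4.7 and 5.6, are redacted and may hold a related analysis. The study is exploratory, and main SAP 5.1 makes no decision rules.

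**Conclusion.** The concern holds in a limited form. Set A labels symptom-triggered days in RT-PCR negatives as well and pools them with healthy days. In every simulated scenario healthy days are about 79% or more of the pool, so its false positive rate is mainly a healthy-day figure. It does not reliably show whether the algorithm separates the three target illnesses from other symptomatic illness: in the 70%/30% example, pooled specificity stays above 60% until ill days exceed 25%. The size rests on assumed symptomatic shares, swab delays and illness lengths, and on counting by day, since the adSAP does not state whether the unit is session, day or participant. With lower healthy-day specificity, or in the bounding case, the pooled figure would fall below 60% and the weakness would show. The primary endpoints are not affected. Given the exploratory aim and the redactions, this is a should-fix and a cheap improvement.

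**What to change.** In adSAP Sections 3, 4.6 and 5.5.1, split Set A:

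- **A1:** negative at both swabs, no new or increased symptoms. The label stays well.
- **A2:** negative at both swabs, with new or increased symptoms triggering swab #2. Label it symptomatic, target-virus negative, and set its illness window by the Primary Analysis Set sick-state rule.

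Report specificity in A1 and A2 with n and 95% CI, beside the pooled figure and the 60% target. State the unit of analysis and the score thresholds for the 5.5.1 table. Say in advance that a claim to detect the target viruses rests on A2, and that adequate specificity in A1 alone supports only a claim to detect symptomatic illness. Bring the copy of the Set A windows in adSAP 4.4 into line.

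Do not remove high-score days from the well windows. That would make the healthy comparator artificially clean and, in the Primary Analysis Set, change the training labels.

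The cost is wording and one more table. The diary and swab data are already collected, although double negatives leave at about Week 6, so late A2 episodes will be cut short. A2 specificity will probably look less favourable than the pooled figure.

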4. GENERAL METHODOLOGY AND CONVENTIONS

4.1. Hypotheses and Decision Rules

Given the algorithm's intended use as a screening tool in the general population not guided by a healthcare professional, we would define the success criteria for the algorithm as achieving a sensitivity on par with that of a rapid antigen test for SARS-CoV-2 infection as observed in real world studies, which is between 60% and 80%¹. Hence, the success criteria for the algorithm will be an observed sensitivity of 70% or better.

The specificity of the algorithm will be assessed with a target minimum specificity of 60% as observed in other studies that use audio signals to detect SARS-CoV-2 infection². The goal is to optimize the sensitivity of the algorithm as the primary performance measure without compromising the minimum specificity, since this algorithm is meant to be used as a screening tool (high sensitivity) and not a diagnostic tool. The reference rapid antigen test benchmarks compared to RT-PCR test for SARS-CoV-2 are as follows¹: sensitivity $\geq 80\%$ in symptomatic individuals and sensitivity $\geq 60\%$ in asymptomatic individuals.

The probability that the observed sensitivity for symptomatic RT-PCR positive participants in AcRIS is greater than 70% with a total number of 100 cases is given in the following table for two assumed true values of expected sensitivity.

Table 1. Probability that observed sensitivity in symptomatic RT-PCR positive participants in AcRIS is greater than 70% with total of 100 cases.

[figure not shown]
True Sensitivity	Probability of Observed Sensitivity > 70% ¹
60%	0.02
75%	0.88
80%	0.99

Thus, with at least 100 symptomatic RT-PCR positive participants in AcRIS, we hypothesize that the study has high probability of success under these conditions.

Furthermore, Figure 1. illustrates the number of cases required to achieve target sensitivity values for a given screening tool – e.g., for a sensitivity of 70% with 10% margin of error for the 95% confidence interval (i.e., 60% to 80%), 81 cases are required (assuming a binomial distribution for the sensitivity values). Identifying 100 symptomatic positive cases should allow us to attain 70% target sensitivity with precision of 8.98%.

¹ Under the assumption of a binomial distribution.

Figure 1. Estimation of the number of cases required to achieve target sensitivity values assuming a 10% margin of error.

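### Meeting the 70% sensitivity criterion in adSAP 4.1 would not show parity with a SARS-CoV-2 antigen test, because the visible cases are symptomatic only and pool three viruses

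*SAP*

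**What the plan says.** All references are to SAP Appendix A (adSAP) unless stated.

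- **Target condition.** Section 1 describes a "screening algorithm for Symptomatic COVID-19 illness".
- **Meaning of success.** Section 4.1 starts from general-population screening and defines success as "achieving a sensitivity on par with that of a rapid antigen test for SARS-CoV-2 infection as observed in real world studies", given as between 60% and 80%. It then sets the rule: "Hence, the success criteria for the algorithm will be an observed sensitivity of 70% or better".
- **Benchmark by symptom status.** The next paragraph of 4.1 lists the antigen-test figures against RT-PCR for SARS-CoV-2: "sensitivity $\geq 80\%$ in symptomatic individuals and sensitivity $\geq 60\%$ in asymptomatic individuals".
- **Cases.** The Primary Analysis Set (section 3) takes participants negative at swab #1 "who become positive for SARS-CoV-2, influenza virus, or RSV (at swab #2) and symptomatic during the study". Secondary Analysis Set B, the additional sensitivity set, also requires symptoms and accepts any of the three viruses. Table 1 in 4.1 is titled for symptomatic RT-PCR positive participants.
- **By-virus results.** The covariate analysis in 5.7 gives age, gender, race and smoking status as examples; virus is not among them. Main SAP 6.4 allows a split by virus of the main SAP 6.1.1 analyses if numbers suffice. Protocol 9.5 says individual-virus and pooled analyses will be assessed if feasible. No visible text commits to a sensitivity for SARS-CoV-2 alone.

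**The concern.** The criterion and its justification refer to different groups. The 60% and 80% ends of the quoted range match the plan's own figures for asymptomatic and symptomatic people, and 70% lies midway. No asymptomatic case enters the visible sensitivity estimates, so the figure for the population actually studied is the one for symptomatic people, at least 80%.

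The comparator and the stated target are also specific to SARS-CoV-2, while the numerator and denominator of the sensitivity include influenza and RSV.

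What is at stake is the meaning of a pass. An algorithm that meets the criterion could be described as matching an antigen test for COVID-19 although its sensitivity is clearly below the plan's own figure for symptomatic people, or although it detects SARS-CoV-2 less well than the pooled figure suggests.

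**Working it through.** **Inputs.** From adSAP 4.1: threshold 70% observed, 100 cases, benchmarks 80% and 60%, Table 1 values, 81 cases for a 10% margin, precision 8.98%. From adSAP 4.2.5.1 and 4.2.6.3: a hold-out of, for example, 20%, so about 20 of 100 cases. The virus mix among cases is not given.

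**1. Reproduce the plan's figures.** The normal approximation to the binomial, 1 − Φ((0.70 − p)/√(p(1 − p)/100)), gives:

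| True sensitivity | Plan, Table 1 | Normal approximation | Exact P(X ≥ 70) | Exact P(X ≥ 71) |
|---|---|---|---|---|
| 60% | 0.02 | 0.021 | 0.025 | 0.015 |
| 75% | 0.88 | 0.876 | 0.896 | 0.850 |
| 80% | 0.99 | 0.994 | 0.994 | 0.989 |

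The number of cases is 1.96² × 0.7 × 0.3 / 0.10² = 80.7, so 81. The half-width at 100 cases is 1.96 × √(0.21/100) = 8.98%. All of the plan's figures reproduce; the arithmetic is not in dispute.

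**2. Where the threshold sits.** (60% + 80%)/2 = 70%. It is the figure for neither group.

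**3. Passing while below the symptomatic figure.** Under the stated rule (70 or more of 100), the exact probability of a pass is 0.549 at a true 70% and 0.896 at a true 75%. Table 1 itself gives 0.88 at 75%, five points under the plan's figure for symptomatic people.

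**4. Does a pass exclude 80%?** 95% intervals:

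| Observed | Exact | Wilson | Excludes 80%? |
|---|---|---|---|
| 70/100 | 60.0% to 78.8% | 60.4% to 78.1% | Yes |
| 71/100 | 61.1% to 79.6% | 61.5% to 79.0% | Yes |
| 72/100 | 62.1% to 80.5% | 62.5% to 79.9% | Wilson only |
| 73/100 | 63.2% to 81.4% | 63.6% to 80.7% | No |
| 14/20 | 45.7% to 88.1% | 48.1% to 85.5% | No |

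The plan's own precision gives the same answer for a bare pass: 70% ± 8.98% is 61.0% to 79.0%.

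**5. Pooling (assumed range).** Let w be the SARS-CoV-2 share of cases and t the sensitivity for the other two viruses. Pooled sensitivity is w·s + (1 − w)·t, so a pooled 70% is reached with a SARS-CoV-2 sensitivity of s = (0.70 − (1 − w)·t)/w.

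| w | t = 80% | t = 90% |
|---|---|---|
| 50% | 60% | 50% |
| 70% | 66% | 61% |
| 90% | 69% | 68% |

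For example, (0.70 − 0.5 × 0.90)/0.5 = 0.50.

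**6. Would an observed-80% rule be better?** With 100 cases, exact P(X ≥ 80) is 0.149 at a true 75% and 0.559 at a true 80%. Such a rule would fail an algorithm that truly reaches 80% with probability 1 − 0.559 = 0.44.

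**The case against.** The best defence is that 70% lies inside the quoted real-world range and the intended use is the general population, which would include asymptomatic infection. The plan states its threshold and its precision openly. Its definition of symptomatic (main SAP 6: at least one new or increased symptom during the study) may also differ from that behind the cited benchmark. Pooling was deliberate: the SAP summary of changes says influenza and RSV were added to Set B to match the primary analysis, and the protocol's amended objective covers all three viruses. The study is exploratory, and main SAP 5.1 says no decision rules will be made.

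This explains the choices but does not restore the claim. The visible case sets cannot speak to asymptomatic infection, adSAP 4.1 does set an explicit success criterion with a named comparator, and pooling leaves a comparator for one virus unmatched.

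A reader might infer more than the documents support:

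- *That every case is symptomatic and no SARS-CoV-2 sensitivity is planned.* An analysis set and several analyses in the adSAP are redacted, the list in 5.7 is open, and protocol 9.5 leaves room for by-virus analyses. Only the lack of a visible commitment can be stated.
- *That any pass rules out 80%.* Only 70 or 71 of 100 does so by the exact method (70 to 72 by Wilson), and 14/20 does not.
- *That SARS-CoV-2 will be detected less well.* The mix and the by-virus sensitivities are unknown; step 5 shows what pooling could hide, not what it will hide.
- *That the threshold must become 80%.* Step 6 shows the cost of that rule with 100 cases. The documents do not require it.
- *That the sponsor plans to announce parity.* Parity is the stated basis of the criterion; no such announcement is written into the reporting sections.

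**Conclusion.** The concern holds in this limited form: meeting the 70% criterion does not support the parity on which adSAP 4.1 bases it. The mismatch is in population (midpoint of two groups' figures against symptomatic cases) and in virus (a SARS-CoV-2 comparator against three pooled viruses).

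Its size: an algorithm five points under the plan's symptomatic figure passes with probability about 0.88 to 0.90, and a bare pass has an interval of about 60% to 79%. Both assume that all 100 cases count towards the estimate. On about 20 hold-out cases the interval is too wide to exclude 80%, but it does not establish parity either. The SARS-CoV-2 sensitivity compatible with a pooled 70% is about 50% to 69%, assuming SARS-CoV-2 is 50% to 90% of cases and the other viruses are detected at 80% to 90%. Statements about case sets and planned analyses apply to the unredacted text only.

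**What to change.** In adSAP 4.1:

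- Keep 70% as the target, described as pooled sensitivity for symptomatic SARS-CoV-2, influenza or RSV illness, and delete the justification by parity with a rapid antigen test.
- Align the target condition in section 1 with that description.

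In the adSAP reporting sections:

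- Report sensitivity with a 95% CI for the pooled set and for SARS-CoV-2 cases alone.
- Set the SARS-CoV-2 estimate and its interval beside the plan's figure of at least 80% in symptomatic people, as context and not as a new pass/fail rule.

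The cost is SAP wording and one extra table row; no new data are needed. The claim becomes less favourable, and the SARS-CoV-2 interval will be wide. At 70% sensitivity with 50 to 90 SARS-CoV-2 cases (the mix assumed above, out of 100), the half-width is 1.96 × √(0.21/50) = 12.7 points to 1.96 × √(0.21/90) = 9.5 points. It would be wider still on the hold-out set.

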4.3. Fusion of Classical Machine Learning and Deep Learning Modeling

Methods such as stacking⁵⁴ or bagging²³ may be used to combine the outputs of the classical machine learning and deep learning models. Performance of the combined models will be assessed as detailed in Section 4.2.6.4.

4.4. Well vs. Sick Analysis with Sick State Definition Centered Around Maximum Total Symptom Score

This analysis will investigate the distinction of well and sick states from voice features, with the sick state definition centered around the maximum total symptom score instead of centered around a positive RT-PCR test. For the purpose of this analysis, the sick and well states will be defined as follows:

For participants who have a negative RT-PCR test at swab #1 and a positive RT-PCR test at swab #2:

The **sick state** is defined by considering a window of Electronic Diary data centered around the maximum total symptom score, from 3 days before to 3 days after the maximum total symptom score, with the following conditions:

- If there are less than or equal to 3 days between maximum total symptom score and swab #1, the start of the sick period will be the day of the maximum total symptom score.
- If there are more than 3 days between the maximum total symptom score and swab #1, the start of the sick period must be at least 3 days after swab #1.
- If there are multiple days with maximum total symptom score, consider the one closest to the day of swab #2 as the center of the window.

The **well state** is defined by considering a window of Electronic Diary data around a negative RT-PCR test at swab #1, from 8 days before swab #1 up to 14 days before the maximum total symptom score. If there are less than 14 days between swab #1 and the maximum total symptom score, the well state window ends on the day of swab #1.

For participants who have a positive RT-PCR test at swab #1, the sick state definition is as follows:

The **sick state** is defined by considering a window of Electronic Diary data centered around the maximum total symptom score, from 3 days before to 3 days after the maximum total symptom score.

- If there are multiple days with maximum total symptom score, consider the one closest to the day of swab #1 as the center of the window.

For participants who have a negative RT-PCR test at both swab #1 and swab #2, the well state definition will remain as defined in Section 3, namely:

The **well state** is defined by considering an:

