4.6. Further Model Testing

The best-performing output models from the classical machine learning ([Section 4.2.5](#).) deep learning ([Section 4.2.6](#).), fusion method ([Sections 4.3](#).) and well vs. sick analysis with sick state definition centered around maximum symptom score ([Section 4.4](#).) will be tested on data of:

- (a) Negative cases to get an estimate of the false positive rate.
- (b) Symptomatic positive participants at swab #1 as an additional dataset for testing the sensitivity rate of the models.

CCI [REDACTED]

For the Change From Baseline Analysis ([Section 4.5](#).), the best performing model will be tested on participants who are negative at both swab #1 and swab #2 to investigate the false positive rate of this approach.

CCI [REDACTED]

CCI

CCI

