5.4. Change from Baseline Analysis

- Analysis Set: Participants in Primary Analysis Set ([Section 3](#)).
- Statistical Method: Listed in [Section 4.5](#).
- Summaries: Using the output of the best performing classical machine learning ([Section 4.2.5](#)), deep learning ([Section 4.2.6](#)) or fusion method ([Section 4.3](#)), the following results will be generated for the specified analysis set:
 - Listing of the features used in the final model
 - Summary statistics of the performance measures listed in [Section 4.2.6.2](#). (mean and standard deviation) for classification of sick and well states for the validation set. Results will be presented in a table.
 - The confusion matrix for the test set will be tabulated and a listing of the performance measures provided.

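### The 70% sensitivity criterion names no model, label definition or test set, while up to five routes report a test sensitivity; the 0.02 in Table 1 describes only one prespecified model on 100 cases.

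*SAP*

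**What the plan says.** adSAP 4.1 sets the rule: "the success criteria for the algorithm will be an observed sensitivity of 70% or better". Table 1 in the same section supports it. Its column is headed "Probability of Observed Sensitivity > 70" (per cent), it is computed for 100 cases, and a footnote gives the basis: "Under the assumption of a binomial distribution". The entries are 0.02, 0.88 and 0.99 for true sensitivities of 60%, 75% and 80%. The section concludes that "we hypothesize that the study has high probability of success under these conditions". It also sets a minimum specificity target of 60%.

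Section 5 of the appendix lists the analyses. Each ends in a test-set confusion matrix with performance measures:

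- classical machine learning (5.1), unconditional;
- deep learning (5.2), only where the data are judged suitable;
- fusion of the two (5.2), on the same condition;
- the maximum-symptom-score analysis (5.3), also conditional, which works "with the sick state definition centered around the maximum total symptom score instead of centered around a positive RT-PCR test" (described in 4.4);
- change from baseline (5.4), unconditional, which subtracts each participant's own baseline and reports "Using the output of the best performing classical machine learning", deep learning or fusion method.

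Section 4.6 carries forward "The best-performing output models from the classical machine learning", deep learning, fusion and maximum-score analyses. They are to be tested again, including on participants who were positive and symptomatic at swab #1 (5.5.2).

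**The concern.** Table 1 is the calculation for one sensitivity estimate, observed once. The plan can produce several. Section 4.2.5.2 picks one model within the classical family by cross-validation, but the readable text has no rule for choosing between families. It also does not say whether one pass is enough.

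The routes do not all measure the same quantity. One uses different sick and well windows, and another uses baseline-subtracted inputs. If the result that carries the claim is picked after the test results are known, success could rest on whichever model or label definition passed. The printed 0.02 would then understate the chance of a false success.

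**Working it through.** **Inputs.** Threshold 70%, 100 cases, binomial distribution and true sensitivity 60% (adSAP 4.1 and Table 1). Number of routes: two unconditional, up to five in all (Section 5). Example hold-out of 20% of subjects (4.2.5.1), so about 0.20 × 100 = 20 cases. The between-model correlation is not in the documents and is assumed.

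**Step 1: reproduce Table 1.** The normal approximation is 1 − Φ((0.70 − p)/√(p(1 − p)/100)).

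- p = 0.60: standard error 0.0490, z = 2.04, probability 0.021.
- p = 0.75: standard error 0.0433, z = −1.155, probability 0.876.
- p = 0.80: standard error 0.0400, z = −2.5, probability 0.994.

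These match the printed 0.02, 0.88 and 0.99. The exact binomial values at p = 0.60 are P(X ≥ 71) = 0.0148 for above 70% and P(X ≥ 70) = 0.0248 for 70% or more. The two events must be kept apart, because the criterion says 70% or better while Table 1 tabulates above 70%.

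**Step 2: let any of k models pass, all truly at 60%.** With independent models the chance is 1 − (1 − a)^k, where a is the single-model probability.

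- k = 2: 1 − (1 − 0.0148)² = 0.029, or 1 − (1 − 0.0248)² = 0.049.
- k = 5: 1 − (1 − 0.0148)⁵ = 0.072, or 1 − (1 − 0.0248)⁵ = 0.118.

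Models scored on the same participants will be correlated. This was simulated with a shared Gaussian latent variable per participant. The lower end of each range below is for high correlation (0.8 to 0.9), and the upper end is independence.

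| Models that may claim success | 100 cases, >70% | 100 cases, ≥70% | 20 cases, >70% | 20 cases, ≥70% |
|---|---|---|---|---|
| 1 | 1.5% | 2.5% | 12.6% | 25.0% |
| 2 (unconditional routes) | 2.5-2.9% | 4.2-4.9% | 19-24% | 34-44% |
| 5 (all named routes) | 4.5-7.2% | 7-12% | 28-49% | 47-76% |

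**Step 3: separate the two effects.** Reading down a 100-case column shows the effect of multiplicity. Reading across the first row, from 1.5% to 12.6% or from 2.5% to 25.0%, shows the effect of a small hold-out with a single model. The second effect is larger and has nothing to do with the number of models.

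**The case against.** Several stronger readings are tempting, and the documents do not support them.

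- **That the 0.02 is an error.** It is not. It is right for one prespecified model on 100 cases.
- **That a pass by any model counts as success.** The text does not say so. It leaves the question open.
- **That at least five models will compete.** Only two routes are unconditional. Section 5.5.1 speaks of two models, the best performer from four of the routes and the change-from-baseline model, and 5.5.2 also uses the singular, although 4.6 uses the plural. With two models on the event that Table 1 tabulates, the rise is from 1.5% to at most 2.9%. The covariance variants should not be counted separately: within 4.2.5 they fall under the classical selection step.
- **That symptom-peak days are an easier target.** This is plausible, but the documents give no data. The Section 3 sick window also follows symptoms and may often include the peak.
- **That the high pass rates on 20 cases show the cost of multiplicity.** Much of that comes from the small hold-out, and the 20% split is itself only an example.

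Three general points also have force. The calculation treats sensitivity alone as success; requiring the 60% specificity minimum as well can only lower these probabilities. The main SAP calls the study exploratory, makes no decision rules (5.1) and does not adjust p-values (5.2). Redacted parts of the appendix could contain a rule across families.

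What remains is the missing identification. The exploratory label does not remove it, because 4.1 itself sets a success threshold, prints pass probabilities and concludes that success is likely. Section 4.1 shows no redaction and no pointer to a rule elsewhere.

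**Conclusion.** The concern holds as a gap in specification. The success criterion is not tied to one model, one label definition or one test set, and the probability printed beside it applies only if all three are fixed in advance. If any model may pass at a true 60% on 100 cases, the chance of a false success is about 2.5-3% (>70%) or 4-5% (≥70%) with the two unconditional routes, and about 4-7% or 7-12% with all five. These figures assume that every model is truly at 60% and that the latent correlation lies between 0.9 and 0.

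Separately, if the criterion is judged on an example hold-out of about 20 cases, a single model passes 12.6% or 25.0% of the time, so the 0.02 would not apply even with one model. This should be corrected. It does not invalidate the planned analyses.

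**What to change.** In adSAP 4.1, name the one result to which the 70% criterion applies:

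- sick and well states as anchored to RT-PCR in Section 3;
- one model, chosen across 4.2.5, 4.2.6, 4.3 and 4.5 by cross-validated performance on training participants only, subject to the 60% specificity minimum;
- that model frozen before the hold-out is opened.

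The classical and deep learning sections describe different validation schemes (4.2.5.1 and 4.2.6.3), so the paragraph should also name a common selection measure and the same hold-out participants for all families. Report every other model without a success claim, including the maximum-score analysis and the results in swab #1 positives.

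If the sponsor prefers to let several models claim success, restate the 60% row of Table 1 for that number of models and for the actual number of test cases.

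The cost is one paragraph, with no new data or analyses. A success claim becomes slightly harder to reach.
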